This research will enroll 225 adult smokers in a mixed design study with a withinsubjects factor (active nicotine patch vs. placebo patch) and a between-subjects factor (alternative products; VLNCs, Juul e-cigs, or no product). Participants will be randomized to receive either 4 weeks of VLNCs, 4 weeks of Juul e-cigs, or no alternative product. After one week practicing with the alternative product, participants will complete the first of two 7-day switching trials during which they will be asked to refrain from smoking their own cigarettes and encouraged to use the alternative product to which they have been assigned (although the no alternative product group will not have any other products to use). See Figure 3. All participants will be given 8 patches (active nicotine or placebo, in counterbalanced order, with one extra in case of mishaps) to use during the Switch Week. After this first Switch Week, they will smoke normally for one week and then have their second Switch Week using the other type of patch (active or placebo; see Figure 3). We opted to use a 7-day switching phase and only repeat it once to minimize the attrition that was problematic in other studies with longer experimental phases (e.g., three 10-day switching phases produced 45% attrition in the non-step down VLNC group¹¹²). Participants will complete ecological momentary assessments (EMAs) on smartphones at prior to and during the 4 weeks of product use. EMA targets include own cigarette use, alternative product use, withdrawal symptoms, rewarding value of product use (e.g., taste, buzz), and environmental and affective context of any tobacco product use. We will then conduct a 3-month follow-up to assess own cigarette and e-cig use, risk perceptions, and future use intentions. This design addresses the six critical methodological issues for understanding the impact of alternative products outlined by Villanti et al.¹¹³: 1) rigorously assesses the key outcome (conventional cigarettes smoked); 2) assesses product use during switching; 3) uses appropriate control/comparison groups; 4) measures product exposure/use that precedes switching; 5) evaluates the dose and duration of the product exposure/use; and 6) has clear evaluation of the type and quality of the products used (e.g., satisfaction).

This mixed design study (within-subjects Patch factor: active nicotine and placebo patch; between-subjects Product factor: VLNC, e-cigarette, or no alternative product) will allow us to address key questions identified in the RFA-OD-18-002. Specifically, we will assess the potential "impact of novel and/or potential modified risk tobacco products on tobacco behavior" and provide data that estimates the real-world impact of potential regulatory actions. To address these questions, this research will focus on the following aims:

Primary Aim: Examine the ability of VLNCs and e-cigarettes to substitute for smokers' usual cigarettes compared to each other and to no alternative product use in real-world settings (between-subjects effects) and whether these effects are influenced by active nicotine replacement (interaction with within-subject factor).

Secondary Aims: Examine the main effects of VLNCs and e-cigarette use compared to each other and to no product use as well as their interaction with active vs. placebo patch on: 1) the use of study alternative products, and 2) mechanisms underlying product use (e.g.,

"Understanding the real-world impact of the use of three alternate nicotine-delivery products on combustible cigarette use" PI: [name]; UW-CTRI Grant: R01CA239309

withdrawal alleviation, taste, satisfaction). We will also explore the contexts that promote or inhibit switching from conventional cigarettes to alternative products and whether participants' risk perceptions and key person factors (e.g., gender, race, education, psychiatric comorbidity) influence switching, alternative product use, and the potential mechanisms that drive such use behavior.

Recruitment and Study Entry

Participants from the greater Madison and Milwaukee, WI areas will be recruited via media recruitment methods (i.e., TV, newspaper, and earned media) that have recruited thousands of smokers^{86,87}. We will also use Internet/paid Facebook advertisements that have been successful in our recent e-cig studies that recruited 422 smokers willing to provide EMA data during seven 2-week assessment periods over 2 years¹⁰¹ and 74 dual users willing to reduce combustible cigarette use and switch to using only e-cigs⁵⁰. Specifically, we will place Facebook ads in the Madison and Milwaukee markets, with keywords likely to reach smokers in the general public. Facebook will charge us per click on the ad. We do not plan to target a specific subpopulation beyond smokers in general. Finally, we will use word of mouth referrals from participants. We believe it is feasible to recruit 225 smokers for this study within 18 months.

Interested individuals will be asked to call the study telephone number and leave their name and telephone number, or leave their name and contact information on our secure website link from the Facebook page, to be called for a phone screen. Potential participants who pass the phone screen will be invited to attend a study session at the UW-CTRI Madison or Milwaukee office, where they will learn more about the study, have eligibility confirmed, and provide written informed consent.

Inclusion/Exclusion

Eligibility criteria include: 1) \geq 21 years old; 2) able to read and write English; 3) no plans to quit smoking in the next 30 days; 4) not currently taking smoking cessation medication; 5) willing and medically able to use nicotine patches, very low nicotine cigarettes, and e-cigarettes; 6) not currently in treatment for psychosis or bipolar disorder; 7) smoking \geq 5 cigarettes per day for the past 6 months; 8) exhaled carbon monoxide (CO) > 5 ppm; 9) no e-cig use within the last month; and 10) not currently pregnant or breastfeeding. We chose to exclude recent e-cig users to minimize the likelihood that participants would chose to use their own e-cig vs. the study ecig. We opted not to exclude ever e-cig users to enhance the external validity of these findings. Analyses will examine the influence of prior e-cig use. It should be noted that use of other tobacco products (e.g., cigars, chew, snus) will not be exclusionary to enhance the external validity of the findings, but we will track such use. Incarcerated individuals will not be enrolled in this study. If study staff members learn that a participant is incarcerated at a time point subsequent to enrollment, the participant will be withdrawn.

Study Visits and Phone Contacts

Interested smokers will complete a phone screen to determine initial eligibility. Potentially eligible smokers will attend an Orientation visit where they will receive a detailed description of the study and provide written informed consent. Participants will then provide a breath sample to verify eligibility (CO > 5 ppm). Eligible participants will also be trained to use the smartphone to complete daily assessments, using the training that was effective in our prior research, and will schedule future study visits (see Table 1). At Visit 1, participants will be randomized to receive VLNCs, e-cigs, or no alternative product and will be trained to use the

"Understanding the real-world impact of the use of three alternate nicotine-delivery products on combustible cigarette use" PI: [name]; UW-CTRI Grant: R01CA239309

	Orientation	V1	V2	V3	V4	V5	V6	V7	Call
Day	0	1	8	11	15	22	25	28	
Week	0	1	2	2	3	4	4	5	3 mo
Consent	Х								
Demographics	Х								
Tobacco use history	Х								
Dependence	Х								
Psychiatric history	Х								
Risks perceptions	Х							Х	Х
Future use intentions	Х							Х	Х
Switching Weeks			Switch Week 1			Switch Week 2			
Alternate product use		Х	Х	Х	Х	Х	Х	Х	Х
Smoking	Х	Х	Х	Х	Х	Х	Х	Х	Х
Cigarette and product evaluation	Х	Х	Х		Х	Х		Х	
Carbon Monoxide	Х	Х	Х	Х	Х	Х	Х	Х	
Cotinine		Х	Х	Х	Х	Х	Х	Х	
Ecological momentary assessments	Х	Х	Х	Х	Х	Х	Х	Х	
Adverse health events			Х	Х	Х	Х	Х	Х	

Table 1. Study Assessments

product [if applicable]. The study database will randomize participants, stratified by clinic, gender, and race [White vs. Non-White], to enhance scientific rigor and reproducibility. Participants will use their alternative products as they would like for one week to become comfortable with the product¹¹⁴. Participants will also provide a urine sample for cotinine assessment and be given eight study patches to use during Switch Week 1 when all participants will be asked to abstain from using their own cigarettes for the week. At Visit 2, all participants will complete assessments, provide a breath sample for CO assessment and a urine sample for cotinine assessment, receive feedback on their compliance with the smartphone assessments. All participants will then attend a mid-Switch Week visit (Visit 3) and an end-of-Switch Week visit (Visit 4) to assess biomarkers (a breath sample for CO assessment and a urine sample for cotinine). At Visit 4, the end of Switch Week 1, all participants will be told that they can smoke as usual for a week. In addition, all participants will be given the other type of patch (active or placebo) and asked to use these patches at the start of Switch Week 2 (Visit 5) when they are asked to abstain from smoking their own cigarettes for a week. As during the prior Switch Week, all participants will attend visits mid-week and at the end of the week to assess biomarkers (Visits 6 and 7). To enhance reproducibility, we will attempt to schedule appointments at the same time of day (i.e., within a 2-hour window) for each participant so that there is consistent time for product use prior to providing the biological samples across study visits. We opted to use a 7-day switching period to provide a stronger test of the ability of these alternative products to substitute for cigarettes than in our prior study⁵⁰ (A.5.1), but to minimize the retention problems seen in studies with longer switches¹¹². There are also strong theoretical and empirical reasons to suspect that withdrawal and other motivations for cigarette use will be strongest in the first 7 days of switching, and this design will allow sampling of the full range of work/nonwork environments for most participants¹¹⁵. Participants will complete a follow-up assessment call at 3 months. The baseline visit will last 2 hours, but subsequent visits will last <30 minutes.

"Understanding the real-world impact of the use of three alternate nicotine-delivery products on combustible cigarette use" PI: [name]; UW-CTRI Grant: R01CA239309

Participants will carry a smartphone to complete EMAs from Orientation through all 4 weeks of product use.

After providing consent at the Orientation visit, study staff will ask if the participant gives the study permission to stay in touch with them and send them reminders about upcoming study contacts during the study via email and/or text message. The staff member will remind them that email and text messaging are generally not a secure way to communicate about their health as there are many ways for unauthorized users to access email and text messages. The staff member will also inform them that they do not have to provide their email address or text message number to participate in this study.

Assessments

To address the primary aim of examining whether VLNCs and e-cigs serve as effective substitutes for conventional cigarettes, and whether use of these alternative products interacts with nicotine replacement, we will conduct extensive assessments of participants' use of their own cigarettes, their use of their assigned alternative products, use contexts, and potential motivators for such use behavior (e.g., withdrawal, reward value of products, risk perceptions). We will also assess person factors and beliefs that may provide insight into who is able and willing to use these alternative products to substitute for cigarettes and which mechanisms might be more relevant for which smokers. To the extent possible we will use measures from the PhenX Toolkit, a collection of broadly validated measures, to enhance the ability to harmonize data from this study with other studies. See Table 1 for the timing of assessments.

Baseline assessments. At the Orientation visit, participants will complete assessments of basic demographics, motivation and self-efficacy for smoking cessation, and tobacco use history using items from our previous research^{86,87,121} and the PhenX Toolkit. This will include a detailed assessment of the timing and use of all non-cigarette tobacco and nicotine products. We will assess lifetime and past year psychiatric comorbidity using a validated self-report instrument¹²² as well as psychiatric vulnerability using the validated self-report Anxiety Sensitivity Index-III and the Distress Tolerance Survey. We will also assess alcohol and marijuana use. Participants will complete two validated measures of cigarette dependence, the Fagerström Test of Cigarette Dependence (FTCD^{123,124}) and the Brief Wisconsin Inventory of Smoking Dependence Motives (Brief WISDM¹²⁵). We will assess risk perceptions of conventional cigarettes, VLNCs, e-cigs, and patches using items that target the four key constructs identified by the Tobacco Centers of Regulatory Science (TCORS) network: 1) perceptions of benefits, 2) harm perceptions, 3) addiction perceptions, and 4) perceptions of social norms¹²⁶. These assessments will be repeated at Visit 7 and the 3-month follow-up call. We will also assess future intentions to use VLNCs, e-cigs, and the patch.

Visit assessments. At each study visit, participants will complete assessments of affect using the well-validated Positive and Negative Affect Scale (PANAS¹²⁷), withdrawal symptoms using the validated Wisconsin Smoking Withdrawal Scale (WSWS¹²⁸), and craving using the Brief Questionnaire of Smoking Urges (QSU-Brief^{129,130}) from the PhenX Toolkit. At Visits 1 through 7 participants will complete the modified Cigarette Evaluation Scale (mCES^{71,131,132}) for cigarettes and at Visits 2 through 7 they will complete the mCES for their assigned alternative product based on their reactions in the last 24 hours. The 12 items of the mCES assess product satisfaction, psychological reward, aversion, enjoyment of respiratory tract sensations, and craving reduction. We will use timeline follow-back methods^{133,134} to assess daily use of participants' own cigarettes, assigned alternative products, and patch if the visit occurs during a Switch Week. These data will be used to supplement EMA reports in case of missing EMA data. Participants will also be asked at all visits except Visit 1 (when they will not have any study products or medication yet) about any possible adverse events from using VLNCs, e-cigs or the patches¹³⁵. At the final visit (Visit 7), we will again assess acceptability, risk perceptions, and

"Understanding the real-world impact of the use of three alternate nicotine-delivery products on combustible cigarette use" PI: [name]; UW-CTRI Grant: R01CA239309

intentions to use cigarettes, VLNCs, e-cigs, and patches. We will also assess how the Juul e-cig compares to other e-cigs participants have used, including what they like or do not like Juul, using a combination of questionnaires and open-ended questions to provide additional information regarding Juul acceptability among adults.

The primary outcome in this research is the number of their own cigarettes participants smoke during the Switch Weeks, although we will also examine the proportion of cigarettes replaced as a tertiary outcome. We will be clear with participants that we want them to do their best to switch completely from their own cigarettes during the two Switch Weeks, but that it is very important for us to know if, and when, they smoke any of their own cigarettes. Research has shown that self-reports of switching behavior are higher than biochemically confirmed reports of switching^{84,136}, given the high rates of non-compliance and misreporting³⁰. To enhance the validity and scientific rigor of the self-report of smoking their own cigarettes, we will conduct carbon monoxide (CO) and cotinine assays. Participants will be told that these tests are used to reflect conventional cigarette and alternative product use, and we will emphasize the importance of accurate reporting of cigarette and alternative product use.

We cannot biochemically verify abstinence from conventional cigarettes in this research due to the experimental conditions and the clearance rates of CO and cotinine. Specifically, we cannot biochemically verify complete substitution in the VLNC group during the active patch Switch Week because VLNCs still produce CO and cotinine is a nicotine metabolite that cannot distinguish the source of nicotine (i.e., from a combustible cigarette vs. a nicotine replacement product). Further, CO can be used to biochemically verify abstinence only within the last 12-18 hours, given its short half-life (4.5 hours¹³⁷), making it impossible to verify smoking that might have occurred more than one day prior to the assay. Cotinine's half-life is 10-30 hours¹³⁸, making it impossible to detect recent abstinence from nicotine products. Therefore, at each visit, participants will provide a breath sample for CO assessment and a urine sample for cotinine assay to evaluate changes in exposure to combustible and nicotine products. Trained study staff at UW-CTRI will collect the participant's urine and follow procedures according to NicAlert directions (see product insert) to get a test reading within the same day. All samples and test results will be labeled with the date of collection and the subject's numerical ID. Urine will be disposed of after cotinine levels are read and recorded.

We will use an exhaled CO < 6 ppm to indicate recent abstinence from combustible products, based on Perkins' cut-off of <5 ppm using a Breathco CO monitor¹³⁹, which is similar to the Vitalograph brand, and produces CO values approximately 1-2 ppm lower than the Bedfont Smokerlyzer monitors¹⁴⁰ we will use in this research. Cotinine will be assessed using NicAlert strips, an immunochromatographic assay that uses monoclonal antibody-coated gold particles and a series of avidity traps to quantify cotinine level. We will use the <100 ng/ml cut-off for non-tobacco users recommended by NicAlert to indicate abstinence from nicotine. The NicAlert strips have 91% specificity and 92% sensitivity at this cut-off compared to liquid chromatography-mass spectrometry¹⁴¹. To maintain the patch double-blind and enhance the scientific rigor, study staff who have no contact with participants will conduct the urine assays.

Ecological momentary assessments. We will assess cigarette and alternative product use in real time in the real-world environment (i.e., ecological momentary assessment [EMA]) using a smartphone app we have used in our prior research. Participants can choose to have the app downloaded on their own smartphone or they will be given a smartphone at the Orientation visit and will be trained to press a button marked "Cigarette" every time they start a new cigarette and to press one marked "JUUL" or "Study Cigarette" every time they use a VLNC or e-cig (which they will be able to use after Visit 1). Participants randomized to receive no alternative product will just record their cigarette use. Daily, each time someone presses a product use button (either to say they used the alternative product or to say they smoked their

"Understanding the real-world impact of the use of three alternate nicotine-delivery products on combustible cigarette use" PI: [name]; UW-CTRI Grant: R01CA239309

own cigarette), there is approximately a 30% chance a more comprehensive assessment (3) minutes) will be triggered that will include: 1) time since prior use of cigarette/alternative product), 2) use context (e.g., smoking prohibited, others vaping/smoking, home, work), activity, and withdrawal symptoms and affect prior to use, and 3) individual items from the mCES that tap potential mechanisms (e.g., product satisfaction, psychological reward, aversion, enjoyment of respiratory tract sensations, and craving reduction). The comprehensive assessments will be specific for each type of use event (i.e., cigarettes, VLNCs, and e-cigs). All participants will complete an evening assessment prior to going to bed. Evening reports (5 minutes) will assess: affect, withdrawal, use of cigarettes and alternative products, overall satisfaction with cigarettes/alternative products, use of patch during Switch Weeks, smoking cues, stressors, and pleasure in daily activities. Participants will spend less than 25 minutes each day recording use events and answering questions, eliminating the problems of recall bias or participants prefilling or back-filling a traditional daily diary. This approach is more rigorous than relying on participants to document their use of non-experimental products using a paper and pencil log¹⁴². We have conducted numerous EMA studies and will use the strategies that have been successful in our earlier work: training in assessments, ability to briefly postpone assessments, use of counters, etc.^{50,86,143}. This frequency of assessment is of moderate intensity relative to protocols used in our prior work⁸⁶.

Follow-up assessment call. Three months after Visit 1, participants will complete a brief follow-up assessment call to assess current smoking, use of any alternative products, motivation and self-efficacy for smoking cessation, risk perceptions, and future plans to use VLNCs, e-cigs, and patches.

Participants who are interested in quitting smoking after Visit 7 will be offered the Wisconsin Tobacco Quit Line toll-free number? ([name]) and the phone number(s) for smoking cessation studies being conducted at our Center.

Alternative Products and the Nicotine Patch

The goal of this research is to examine the potential impact of alternative tobacco products on the use of conventional cigarettes, alone and in combination with nicotine replacement, to simulate a potential regulatory scenario in which a variety of tobacco and nicotine products are available that vary in degree of risk, similarity to cigarettes, and acceptability. Therefore, we opted to use two products that have shown potential to substitute for traditional cigarettes: very low nicotine content cigarettes (VLNCs) and the Juul e-cig.

VLNCs. Participants randomized to receive VLNCs will receive NIDA's reduced nicotine cigarettes with 0.03 (±0.01) mg of nicotine with a tar yield of 9±1.5 via NIDA's Drug Supply Program (NOT-DA-14-004). These cigarettes have been characterized by Richter and colleagues¹¹⁶. Participants will be able to choose either menthol or non-menthol VLNC's consistent with prior research (e.g., ¹⁰⁰) and to enhance the external validity of these findings. Participants will be instructed to smoke the VLNCs the same way they would their own cigarettes and will be given enough VLNCs to completely substitute for their own cigarettes during the Switch Weeks (i.e., if they smoke 20 cigarettes per day, they will receive enough VLNCs to be able to smoke 20 VLNCs per day).

One real-world safety concern with VLNC use is that it might result in compensatory smoking or oversmoking and increased exposure to carcinogens¹¹⁷. However, many studies have shown that smokers engage in minimal or no compensatory smoking^{73,82,83,102,118}. If participants in this condition need more VLNCs, they will be provided with additional VLNCs at subsequent study visits. However, we will monitor compensatory smoking by examining both VLNCs smoked/day as well as carbon monoxide (CO) levels. Participants found to be smoking more than twice their usual cigarettes/day or who demonstrate a CO \geq 100 ppm will be

"Understanding the real-world impact of the use of three alternate nicotine-delivery products on combustible cigarette use" PI: [name]; UW-CTRI Grant: R01CA239309

discontinued from the study protocol. Research has also shown that there is no increased risk with respect to cardiovascular biomarkers or exposure to toxicants among smokers using VLNCs^{67,97,119,120} and this study will produce a very brief exposure (i.e., only 4 weeks, which is less than the 6 weeks used by other studies^{67,83,97}).

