The secondary outcome is number of VLNCs or JUUL pods used during each switch week. This research will also examine the main effects for Product and Patch and the Product X Patch interaction effect on other exploratory outcomes: 1) the proportion of conventional cigarettes replaced; 2) the use of alternative tobacco products; 3) use contexts; and 4) potential mechanisms such as rewarding value of the alternative products and conventional cigarettes, alleviation of withdrawal symptoms, and taste. We will also explore the impact of person factors (e.g., sex, education, psychiatric comorbidity, dependence) and risk perceptions on the primary, secondary, and exploratory outcomes. We will include these variables as covariates in the analyses, and we will include covariate interaction terms with the between- and within-subjects factors (e.g., sex x Product; sex x Product x Patch) to determine whether these individual difference variables moderate the ability of the alternative products to substitute for conventional cigarettes. To examine use contexts and putative mechanisms driving alternative product use and substitution for conventional cigarettes, we will use the daily EMA data from the evening reports as well as data from the quasi-random daily assessments that will be collected during the Switch Weeks as described above as the exploratory outcome variables. One set of analyses will test summary versions of the outcomes (e.g., means or counts across the Switch Weeks); another set of more fine-grained analyses will preserve the intensive longitudinal data (ILD) aspect of the EMA data collected during each of the 7 days of the Switch Weeks. For the summary versions of the outcomes, the alternative product use outcome will consist of the mean alternative product use events per day reported during the Switch Weeks and the context

"Understanding the real-world impact of the use of three alternate nicotine-delivery products on combustible cigarette use" PI: [name]; UW-CTRI Grant: R01CA239309

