and mechanisms variables will be based on means across the 7 days of the Switch Weeks. For these summary outcomes, we will use statistical models similar to the analyses described above for the primary outcome. For the ILD outcomes, we will create one set of outcomes based on the evening report that assesses experiences across the full day and another set based on the 3 quasi-random comprehensive assessments that occur during the day. For the ILD versions of the outcomes, we will use conditional growth curve models that permit slope and intercept parameters to be evaluated across the 7 days of the Switch Weeks as a function of group; these models also permit examination of other forms of change over time (e.g., linear, quadratic, cubic). We will explore two main approaches to growth curve modeling: a multilevel modeling (MLM) approach¹⁵⁸ and a structural equation modeling (SEM) approach¹⁵⁹. Although similar, each of these modeling approaches has advantages and disadvantages¹⁶⁰ that we will exploit in exploratory analyses. While we are not powered to detect mediation due to funding limitations, we will conduct exploratory mediation analyses to provide information for future research on whether these mechanisms mediate the effects of alternative product use on the use of conventional cigarettes.

Power for Primary Aim Hypotheses

With attrition-adjusted n=54 per group for a between-subjects pairwise comparison, the study is powered to detect a difference of 3.3 cigarettes (SD=6); a corresponding within-subjects pairwise comparison (SD=6, correlation=0.5) is powered to detect a difference of 2.8 cigarettes. Thus, we feel that a total N=225 provides adequate power to detect predicted effects.

Protection of Human Subjects

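### No planned model relates context to whether an own cigarette or the study product is used, so the exploratory aim on contexts that promote or inhibit switching is not directly estimated

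*Combined protocol and SAP*

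**What the plan says.** The Secondary Aims paragraph adds an exploratory question: "We will also explore the contexts that promote or inhibit switching from conventional cigarettes to alternative products". Here context is the influence and switching is the result.

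The Analytic Plan then handles context as follows.

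- It is one of a set of outcomes: "This research will also examine the main effects for Product and Patch and the Product X Patch interaction effect on other exploratory outcomes", a list that includes "3) use contexts; and 4) potential mechanisms such as rewarding value of the alternative products and conventional cigarettes".
- The stated purpose is wider: "To examine use contexts and putative mechanisms driving alternative product use and substitution for conventional cigarettes, we will use the daily EMA data". The same sentence, however, gives those data their role: they are "collected during the Switch Weeks as described above as the exploratory outcome variables".
- In summary form, the context "and mechanisms variables will be based on means across the 7 days of the Switch Weeks", and for such summaries "we will use statistical models similar to the analyses described above for the primary outcome". That means the mixed ANOVA with three Product levels and two Patch levels.
- In intensive longitudinal form, the outcomes go into growth curves over the seven days, compared by group.

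The Ecological momentary assessments section describes the raw material. Each button press, for an own cigarette or for the study product, has about a 30% chance of triggering a longer assessment. That assessment records where and with whom the use took place, and withdrawal and affect beforehand. "The comprehensive assessments will be specific for each type of use event", so context is recorded separately for own-cigarette, VLNC and e-cigarette events in the same person.

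**The concern.** The aim asks whether a setting (smoking not allowed, other users present, home, work) makes a person more or less likely to use the study product instead of an own cigarette. A Product or Patch difference in mean context answers another question: whether the arms' use took place in different settings. Two arms can have the same mean context while context strongly governs which product is picked up within each person.

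What is at stake is interpretation of an exploratory result. A null Product or Patch comparison of context could be reported as evidence that context does not matter for switching, when the comparison was not built to show it. The event-level data that could show it would go unused for this purpose.

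**Working it through.** The plan gives no figure for this point, so there is none to reproduce. The check has three parts.

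**1. Do other planned models fill the gap?** The primary model has own cigarettes as outcome and Product and Patch as factors. The covariates and moderators are person factors and risk perceptions, and the Inclusion/Exclusion section adds prior e-cigarette use. The exploratory mediation analyses concern mechanisms. Context is an explanatory term in none of these, and event type (own cigarette or study product) is not named as a factor in any model of context.

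**2. What the planned comparison can see.** Let *c* be the share of use events in a given context (assumed 0.30 in every arm), *a* the probability that a use event outside that context is an own cigarette, and *o* = *a*/(1 − *a*). With a within-person odds ratio OR common to both product arms:

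- P(own | context) = OR·*o* / (1 + OR·*o*)
- own-cigarette share *s* = (1 − *c*)·*a* + *c*·P(own | context)
- context share among own-cigarette events = *c*·P(own | context) / *s*

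Two assumed values of *a* give own-cigarette shares of roughly 17–48%:

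| *a* | OR | P(own \| context) | *s* | Context share, all events | Context share, own-cigarette events |
|---|---|---|---|---|---|
| 0.50 | 0.5 | 0.333 | 0.35 + 0.100 = 0.450 | 30% | 0.100/0.450 = 22.2% |
| 0.50 | 0.8 | 0.444 | 0.35 + 0.133 = 0.483 | 30% | 0.133/0.483 = 27.6% |
| 0.20 | 0.5 | 0.111 | 0.14 + 0.033 = 0.173 | 30% | 0.033/0.173 = 19.2% |
| 0.20 | 0.8 | 0.167 | 0.14 + 0.050 = 0.190 | 30% | 0.050/0.190 = 26.3% |

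Pooled over all events, mean context is 30% in every arm whatever the OR, so a Product or Patch test has nothing to find. Restricted to own-cigarette events, the product arms differ from the no-product arm (30%) by 7.8–10.8 points at OR 0.5, but only 2.4–3.7 points at OR 0.8.

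**3. Rejection rates by simulation.** From the plan: 54 per arm (the attrition-adjusted figure in the power section), two Switch Weeks and a 30% trigger. Assumed: context at about 30% of events, the same context effect in both product arms, and test level 5%. Twenty uses a day give 20 × 0.30 = 6 assessments; ten give 3, which matches the Analytic Plan's mention of three quasi-random assessments a day. There were 200–300 runs per setting where the count is recorded.

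| Test | OR 0.5 | OR 0.8 |
|---|---|---|
| Context pooled, two product arms, Product / Patch, 6 a day | 5% / 2% | 6% / 5% |
| Context pooled, three-arm Product / Patch in product arms, 6 a day | 6% / 4% | 5% / 4% |
| Context pooled, three-arm Product / Patch in product arms, 3 a day | – | 5% / 6% |
| Own-cigarette context, three-arm Product, 6 a day | 76% (30% at OR 0.67) | 12% |
| Own-cigarette context, three-arm Product, repeat simulation | 76–91% | 14–15% |
| Own-cigarette context, three-arm Product, own share about 17% or 46%, between-person context SD 0–1 logit, 3 or 6 a day | 36–100% | 8–28% |
| Within-person event-level test, 6 a day | 100% | 93–97% |
| Within-person event-level test, 3 a day | – | 67–81% |
| Within-person event-level test, repeat simulation | 100% | 81–98% |
| Within-person event-level test, varied settings as above | – | 56–98% |

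With no context effect (OR 1.0), the pooled tests rejected in 6%, the event-level test in 5% and the own-cigarette test in 2–8%.

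A day-level version (1,000 runs per setting, context distributed identically in all arms) set the effect on own cigarettes per day at 0, −3, −6 or +6 per unit of context share. Context compared by Product rejected in 3.8–5.6% of runs and by Patch in 4.1–6.3%, whatever the effect. A within-person model with context as predictor rejected in 5.9% at zero effect and 99.9–100% otherwise.

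**The case against.** - **The planned tests are not necessarily blind.** A reader might infer that they must miss a context effect whatever the data show. The documents do not support that. Assessments are specific to event type, so context could be summarised over own-cigarette events, the one type all three arms share. The no-product arm is then a randomised comparator, not a flaw, and large effects are detectable. This stands. But the plan does not say which summary it means, and the own-cigarette version is weak at moderate effects.
- **The side of the model is not the error.** An odds ratio is symmetric: context by event type and event type by context give the same association. This also stands. The gap is that event type is not related to context in any planned model.
- **The pooled null is built in.** The simulations impose equal context distributions and a common effect. Correct: they show what the test can respond to and do not estimate a loss in this trial.
- **Event-level power depends on data volume.** At three assessments a day it is lower, and the Analytic Plan expects that a substantial fraction may smoke no own cigarettes in a Switch Week. Participants with only one event type add little to a within-person estimate. This stands and belongs in the write-up.
- **The aim is exploratory.** The plan keeps event-level data, names multilevel modelling and states an intention to study what drives substitution. Leaving one exploratory model unwritten is common. This limits the weight of the point but does not supply the model.

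**Conclusion.** The point holds in a limited form. Every planned model that uses context compares it by Product, Patch or group, and none relates it to the choice between own cigarette and study product. Pooled over all events, these comparisons stay near the 5% level for a context effect common to both product arms. On own-cigarette events only, the three-arm Product test rejects in about 76–91% of runs at OR 0.5 and 14–15% at OR 0.8 (36–100% and 8–28% across wider assumptions). A within-person event-level test reaches 100% and 81–98% (down to 56% at OR 0.8 in the least favourable setting). Neither planned version estimates how a context shifts a person's choice.

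The sizes rest on assumed context frequency, use rates, own-cigarette share and a common effect, none of which the plan gives. The event-level figures come from a within-person test, not from the multilevel model proposed below.

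A reader might also infer a threat to the trial's main conclusions. There is none: the aim is exploratory, and the primary and secondary outcomes, error rates and sample size are untouched.

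**What to change.** In the Analytic Plan, keep the Product and Patch comparisons of context as description, and say whether they use all events or own-cigarette events. Add one exploratory model:

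- **Data:** each triggered comprehensive assessment in the Switch Weeks, in the VLNC and e-cigarette arms.
- **Outcome:** own cigarette versus study product.
- **Predictors:** the context items and pre-use withdrawal and affect, each split into within-person deviation and person mean; Product; Patch; and context × Product.
- **Model:** multilevel logistic regression with a participant random intercept. The trigger probability is the same for both kinds of press, so this sampling should not distort the odds ratio.
- **Stated limits:** the result is conditional on a use event and does not cover contexts that lead to no use; participants with only one event type add little to the within-person estimate.

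The cost is about one paragraph of SAP text and one extra exploratory analysis. No new data, visits or participants are needed.
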